Appendix 2 List of Permitted and Prohibited Prior/Concomitant Medications

Prohibited medications are shown in [Listing 1](#) through [Listing 5](#). Medications permitted with restrictions are listed in [Listing 6 through Listing 8](#). (revised per Amendment 04) **These may not be all-inclusive listings.** Please contact the medical monitor(s) if the investigators have any questions or concerns regarding any medication not listed that your subjects may be taking before enrollment or start during the course of the E2609-G000-202 study.

Antibiotics, analgesics, and anti-inflammatory drugs intended for short courses of treatment are permitted and do not need to follow the restrictions of [Listing 8](#) for a stable dose of 4 weeks before Baseline. If these medications may affect cognitive function but the medications are clinically indicated, then cognitive testing should not take place until at least 72 hours after the last dose of the course of treatment.

Prohibited Prior/Concomitant Medications

Listing 1 Drugs with High Risk of Torsades de Pointes or QTc Prolongation

| Generic name | Brand name (Names shown are not exhaustive and are examples only; names may be the ® or ™) | Comments |
|---|--|---|
| Prohibited from 14 days (or 5 half-lives, whichever is longer) before Randomization until after the last treatment visit | | |
| Anti-arrhythmic/ abnormal heart rhythm | | |
| Amiodarone | Cordarone; Pacerone | Incidence in females greater than males, Torsades de Pointes risk regarded as low |
| Disopyramide | Norpace | Incidence in females greater than males |
| Dofetilide | Tikosyn | |
| Ibutilide | Corvert | Incidence in females greater than males |
| Procainamide | Pronestyl; Procan | |
| Quinidine | Cardioquin; Quinaglute | Incidence in females greater than males |
| Sotalol | Betapace | Incidence in females greater than males |
| Antihistamine/ allergic rhinitis | | |
| Astemizole | Hismanal | No longer available in United States |
| Terfenadine | Seldane | No longer available in United States |
| Anti-anginal/ heart pain | | |
| Bepridil | Vascor | Incidence in females greater than males |
| Antibiotic/ bacterial infection | | |
| Clarithromycin | Biaxin | |
| Moxifloxacin | Avelox | |
| Sparfloxacin | Zagam | |
| Listing 1 continued | | |
| Antimalarial/ malaria infection | | |
| Chloroquine | Aralen | |
| Halofantrine | Halfan | Incidence in females greater than males |
| Antipsychotic/ anti-emetic/ schizophrenia/ nausea | | |
| Chlorpromazine | Thorazine | |
| Gastrointestinal stimulant/ heartburn | | |
| Cisapride | Propulsid | |

Listing 1 Drugs with High Risk of Torsades de Pointes or QTc Prolongation

| Generic name | Brand name (Names shown are not exhaustive and are examples only; names may be the ® or ™) | Comments |
|--|--|---|
| Antinausea/ nausea | | |
| Domperidone | Motillum | Not available in the United States |
| Sedative; antinausea/ anesthesia adjunct, nausea | | |
| Droperidol | Inapsine | |
| Antibiotic; gastrointestinal stimulant/ bacterial infection; increase gastrointestinal motility | | |
| Erythromycin | Erythrocin; E.E.S. | Incidence in females greater than males |
| Antipsychotic/ schizophrenia | | |
| Haloperidol | Haldol | When given intravenously or at higher than recommended doses, risk of sudden death, QT prolongation, and torsades increases |
| Mesoridazine | Serentil | |
| Thioridazine | Mellaril | |
| Opiate agonist/ pain control, narcotic dependence | | |
| Levomethadyl | Orlaam | |
| Methadone | Methadose; Dolophine | Incidence in females greater than males |
| Anti-infective/ pneumocystis pneumonia | | |
| Pentamidine | Pentam; NebuPent | Incidence in females greater than males |
| Antipsychotic/ Tourette's tics | | |
| Pimozide | Orap | Incidence in females greater than males |
| Antilipemic/ hypercholesterolemia | | |
| Probucol | Lorelco | No longer available in United States |
| Anticancer | | |
| Arsenic trioxide | Trisenox | Used for leukemia |
| Vandetanib | Zactima | Used for thyroid cancer |

Note: This list is not exhaustive.

QTc = Corrected QT interval.

Listing 2 Prohibited Medications Within 5 Half-lives or 60 days, Whichever is Longer, Before Randomization and Until after the Last Treatment Visit

| Generic name | Brand name (Names shown are not exhaustive and are examples only; names may be the ® or ™) |
|---|--|
| Systemic Immunosuppressants^{a,b} and Immunomodulatory therapy | |
| Azathioprine | Azasan, Imur |
| Ciclosporine | Gengraf, Neoral |
| Dexamethasone | Decadron, Dexasone, Diodex, Hexadrol, Maxidex |
| Fingolimod | Gilenya |
| Methotrexate | Trexall |
| Methylprednisolone | Medrol, Meprolone |
| Mycophenolate | CellCept, Myfortic |
| Prednisolone | Deltasone, Prednicot, Prednisone Intensol, Rayos, Sterapred, Sterapred DS |

Note: This list is not exhaustive.

- a: Topical and inhaled formulations with minimal systemic exposure need not be prohibited.
- b: During the treatment period of the study, short term (not more than 14 days) use of steroids up to the equivalent of prednisolone 40 mg OD is permitted after discussion with the Medical Monitor. Dosing with study drug should be suspended from the time steroid treatment is started. Complete blood count and lymphocyte subsets should be determined prior to starting steroid treatment and continue to be monitored weekly. Study drug may be resumed after discussion with the Medical Monitor when the following conditions are met: (1) treatment with steroids has been completed for at least 1 week; (2) absolute lymphocytes not <LLN; (3) no lymphocyte subsets are below the discontinuation threshold (for Core Study only); (4) the investigator considers that the medical condition which required treatment with steroids has improved or resolved. Weekly testing of lymphocyte subset counts (for Core Study only) and CBC with differentials is required for 4 weeks following resumption of study drug administration. (revised per Amendment 04)

Listing 3 Prohibited Medications Within 6 Months Before Randomization

| Generic name | Brand name (Names shown are not exhaustive and are examples only; names may be the [®] or [™]) |
|---|---|
| Immunoglobulin therapy | |
| Adalimumab | Humira |
| Bevacizumab | Avastin |
| Efalizumab | Raptiva |
| Etanercept | Enbrel |
| Immune globulin IV, IVIG, IGIV | Carimune, Flebogamma, Gamimune N, Gammagard, Gamunex, Gammar-P IV, Iveegam, Octagam, Panglobulin, Vigam, Polygam S/D, Privigen, Sandoglobulin, Venoglobulin-S |
| Infliximab | Remicade |
| Omalizumab | Xolair |
| Ranibizumab | Lucentis |
| Other monoclonal antibodies not listed here | |

Note: This list is not exhaustive.

Listing 4 Prohibited Live Vaccines Within 3 Months Before Randomization Until after the Last Treatment Visit (this does not apply to non-live/inactivated vaccines)

| Bacterial vaccines | Viral vaccines |
|---|---|
| Bacillus Calmette-Guérin vaccine against tuberculosis | Measles vaccination |
| Cholera vaccination (oral) | Rubella vaccination |
| | Oral polio vaccination (Sabin) |
| | Yellow fever vaccination |
| | Varicella (chickenpox) vaccination |
| | Rotavirus vaccination |
| | Japanese encephalitis vaccination |
| | Live attenuated influenza vaccine (FluMist, Fluenz) |
| Typhoid vaccination (oral) | Mumps vaccination |

Note: This list is not exhaustive

Listing 5 Strong CYP3A4 Inhibitors Prohibited Within 5 Half-Lives or 14 Days (Whichever Is Longer) Before Randomization Until After the Last Treatment Visit

| Generic name | Brand name(s) |
|----------------|--|
| boceprevir | Victrelis |
| clarithromycin | Clarithromycin, clarithromycin extended release, Prevpac |
| cobicistat | Tybost, Stribild, |
| conivaptan | Vaprisol |
| danoprevir | |
| elvitegravir | Vitekta, Stribild |
| indinavir | Crixivan |
| itraconazole | Sporanoz, Onmel |
| ketoconazole | Xolegel, Nizoral, Ketodan |
| lopinavir | Kaletra |
| nefazodone | Serzone |
| nelfinavir | Viracept |
| posaconazole | Noxafil |
| ritonavir | Norvir, Kaletra |
| saquinavir | Invirase, Fortovase |
| telaprevir | Incivek |
| telithromycin | Ketek |
| tipranavir | Aptivus |
| troleandomycin | Triocetin |
| voriconazole | Vfend, Voriconazole |

Note: This list is not exhaustive

Permitted Prior/Concomitant Medications

Listing 6 Medications Which Need To Be on a Stable Dose for 12 Weeks Before the Baseline Cognitive Assessments at Visit 2 and Remain on the Same Stable Dose from Baseline to Final Follow-Up Visit

| Generic name | Brand name (Names shown are not exhaustive and are examples only; names may be the [®] or [™]) |
|----------------------------|---|
| Cognitive Enhancers | |
| Donepezil | Aricept |
| Galantamine | Reminyl |
| Memantine | Namenda |
| Rivastigmine | Exelon |

Note: This list is not exhaustive.

Listing 7 Permitted Medications Used on PRN Basis Which are Not to be Used Within 72 Hours before Cognitive Testing

| Generic name | Brand name (Names shown are not exhaustive and are examples only; names may be the ® or ™) |
|---|---|
| Opiates | |
| Morphine | Astramorph PF, Avinza, Depo Dur, Duramorph, Infumorph, Kadian, MS Contin, MSIR, Oramorph SR, RMS, Roxanol |
| Opiate Agonists | |
| Codeine | Codeine |
| Fentanyl | Actiq, Duragesic, Fentora, Onsolis, Sublimaze |
| Meperidine | Demerol, Meperitab |
| Oxycodone | Dazidox, Endocodone, Eth-OxyDose, OxyContin, OxyFast, OxyIR, Percolone, Roxicodone, Roxicodone Intensol |
| Other opioids or opioid agonists which are used on PRN basis | |
| Benzodiazepines and sedatives | |
| Alprazolam | Alprazolam Intensol, Niravam, Xanax |
| Amitriptyline | (various) |
| Chlordiazepoxide | H-Tran, Librium |
| Clonazepam | Ceberclon, Klonopin |
| Diazepam | Diastat, Dizac, Valium |
| Dothiepin | (various) |
| Estazolam | ProSom |
| Flunitrazepam | Rohypnol |
| Flurazepam | Dalmane |
| Lorazepam | Ativan |
| Midazolam | Versed |
| Olanzapine | Zyprexa |
| Promethazine | Phenergan; others |
| Ramelteon | Rozerem |
| Risperidone | Risperdal |
| Temazepam | Restoril |
| Triazolam | Halcion |
| Zolpidem | Ambien; others |
| Zopiclone | (various) |
| Other benzodiazepines, tricyclic antidepressants, antipsychotics and other drugs which are used on PRN basis as sedatives | |

Note: This list is not exhaustive

**Listing 7 Permitted Medications Used on PRN Basis Which are Not to be Used
Within 72 Hours before Cognitive Testing**

| Generic name | Brand name (Names shown are not exhaustive and are examples only; names may be the [®] or [™]) |
|--------------|--|
|--------------|--|

PRN = Pro re nata

Listing 8 Permitted Centrally Active or Psychiatric Medications

| Generic Name | Brand name (Names shown are not exhaustive and are examples only; names may be the ® or ™) |
|---|--|
| If to be used on a PRN basis see Listing 7. If to be used chronically, subjects must be on a stable dose for ≥4 weeks before Baseline. Changes in dose or initiation of new concomitant medications for chronic use (not PRN use) is permitted but if the medication affects cognitive function, do not conduct cognitive testing until the dose is stable for 4 weeks. | |
| Antidepressants | |
| Amitriptyline hydrochloride | Elavil |
| Amoxapine | Amoxapine |
| Bupropion | Aplenzin, Budeprion, Buproban, Zyban, Wellbutrin |
| Citalopram | Celexa |
| Clomipramine hydrochloride | Anafranil |
| Desipramine hydrochloride | Norpramin |
| Desvenlafaxine | Pristiq |
| Doxepin hydrochloride | Prudoxin, Silenor, Sinequan, Zonalon |
| Duloxetine | Cymbalta |
| Escitalopram | Lexapro |
| Fluoxetine | Prozac, Sarafem, Selfemra |
| Fluvoxamine | Luvox |
| Imipramine hydrochloride | Tofranil |
| Isocarboxazid | Marplan |
| Maprotiline hydrochloride | Ludiomil |
| Mirtazapine | Remeron Soltab |
| Nortriptyline hydrochloride | Aventyl, Pamelor |
| Paroxetine | Paxil, Pexeva |
| Phenelzine | Nardil |
| Protriptyline hydrochloride | Vivactil |
| Rasagiline | Azilect |
| Selegiline | EMSAM |
| Sertraline | Sertaraline, Zoloft |
| Tranlycypromine | Parnate |
| Trazodone hydrochloride | Desyrel, Oleptro |
| Trimipramine maleate | Surmontil |
| Venlafaxine hydrochloride | Effexor |

Listing 8 Permitted Centrally Active or Psychiatric Medications

| Generic Name | Brand name (Names shown are not exhaustive and are examples only; names may be the ® or ™) |
|---|--|
| Mood Stabilizers (Listing 8 continued) | |
| Carbamazepine | Carbatrol, Epitol, Equetro, Tegretol, Tegretol XR |
| Lamotrigine | Lamictal, Lamictal CD, Lamictal ODT, Lamictal XR |
| Valproic acid | Depacon, Depakene, Depakote, Depakote ER, Divalproex Sodium, Stavzor, Valproate |
| Antipsychotics | |
| Acetophenazine | Tindal |
| Aripiprazole | Abilify |
| Asenapine | Saphris |
| Olanzapine | Zyprexa |
| Chlorpromazine | Thorazine |
| Haloperidol | Haloperidol, Haldol |
| Clozapine | Clozaril, Fazaclo |
| Fluphenazine | Prolixin |
| L-Methylfolate | Deplin, L-Methylfolate Calcium |
| Loxapine | Loxitane |
| Mesoridazine | Serentil |
| Perphenazine | Trilafon |
| Quetiapine | Seroquel |
| Risperidone | Risperdal |
| Thioridazine | Mellaril |
| Thiothixene | Navane |
| Trifluoperazine | Stelazine |
| Benzodiazepines | |
| Alprazolam | Alprazolam Intensol, Niravam, Xanax |
| Chlordiazepoxide | H-Tran, Librium |
| Clonazepam | Ceberclon, Klonopin |
| Diazepam | Diastat, Dizac, Valium |
| Estazolam | ProSom |

Listing 8 Permitted Centrally Active or Psychiatric Medications

| Generic Name | Brand name (Names shown are not exhaustive and are examples only; names may be the ® or ™) |
|---------------|--|
| Flunitrazepam | Rohypnol |
| Flurazepam | Dalmane |
| Lorazepam | Ativan |
| Midazolam | Versed |
| Temazepam | Restoril |
| Triazolam | Halcion |
| Zopiclone | Imovane, Zimovane |
| Zopidem | Ambien, Ambien CR, Intermezzo, Stilnox, Stilnoct, Sublinox, Hypnogen, Zolsana |

Note: This list is not exhaustive.

PRN = Pro re nata

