9.4.7 Prior and Concomitant Therapy

Medication (including over-the-counter medications) or therapy administered to the subject before the study (within 6 months of randomization) and during the study (starting at the date of informed consent) will be recorded on the Prior & Concomitant Medication eCRF or Non-Pharmacological Procedures eCRF. The investigator will record on the Adverse Event eCRF any AE for which the concomitant medication/therapy was administered. If the concomitant medication/therapy is being administered for a medical condition present at the time of entry into the study, the investigator will record the medical condition on the Medical History and Current Medical Condition eCRF.

Listings of prohibited and permitted drugs during the Core Study and OLE Phase are provided in [Appendix 2](#). (revised per Amendment 07) Prohibited medications are presented in [Listing 1](#) through [Listing 5](#). Medications that are permitted with restrictions are listed in [Listing 6](#) through [Listing 8](#). (revised per Amendment 04)

The types of agents listed below are not permitted before randomization unless discontinued according to the specific timeframes as shown below; these types of agents are not permitted during the Core Study or OLE Phase until after the last treatment visit: (revised per Amendments 04 and 07)

- Drugs which may cause QTc prolongation are not permitted for a period of 5 half-lives or 14 days (whichever is longer) before randomization
- Strong CYP3A4 inhibitors are not permitted for a period of 5 half-lives or 14 days (whichever is longer) before randomization
- Live vaccines are not permitted within 3 months before randomization. This does not apply to non-live/inactivated vaccines

- Ig therapy and biologic drugs are not permitted within 6 months before randomization

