Subjects who initiate treatment with or have dose adjustment of drugs not intended for treatment of cognitive impairment during the study may continue in the study if in the opinion of the investigator this will not interfere with study procedures or subject safety, and are not prohibited above. (revised per Amendment 05)

Antiplatelet therapy: (revised per Amendment 04)

- For subjects who consent to CSF sample collection: Either aspirin or clopidogrel (or any other antiplatelet drug which is not aspirin) are permitted in all subjects. Aspirin and clopidogrel (or any other antiplatelet drug which is not aspirin) in combination are also

permitted but subjects who are on such a combination of antiplatelet drugs may be required to stop 1 or more of these antiplatelet drugs before the LP procedure and restart after the LP as per local guidelines.

- For subjects who do not consent to CSF sample collection: Aspirin and clopidogrel, individually or in combination, are permitted.

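### Appendix 2 prohibits four antipsychotics in Listing 1 for torsades/QTc risk and permits the same four, including new starts, in Listing 8

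*Protocol*

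**What the plan says.** Listing 1 of Appendix 2 covers drugs with a high risk of torsades de pointes or QTc prolongation. Its rule is "Prohibited from 14 days (or 5 half-lives, whichever is longer) before Randomization until after the last treatment visit". Chlorpromazine, haloperidol, mesoridazine and thioridazine are all in it.

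Listing 8 of the same appendix sets out the permitted centrally active or psychiatric medications, and its antipsychotic block names the same four drugs. Its conditions are a dose stable for at least 4 weeks before Baseline for chronic use, and a delay in cognitive testing until a drug that affects cognition has been at a stable dose for 4 weeks. It then says: "Changes in dose or initiation of new concomitant medications for chronic use (not PRN use) is permitted". As-needed use is referred to Listing 7.

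The body text agrees with Listing 1. Section 9.4.7 includes drugs that may prolong QTc among the barred classes and says "these types of agents are not permitted during the Core Study or OLE Phase until after the last treatment visit". It allows other drugs to be started during the study if the investigator judges that "this will not interfere with study procedures or subject safety, and are not prohibited above". Exclusion criterion 25 (Section 9.3.2) excludes users of QT-prolonging medication, and criterion 37 excludes violations of the medication restrictions.

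**The concern.** A subject cannot take one of these four drugs under Listing 8 during treatment without breaching Listing 1. Nothing in Appendix 2 says which listing prevails, and Section 9.4.7 itself sends sites to Listings 6 to 8 for drugs allowed with restrictions. A site that looks up an antipsychotic in the listing written for psychiatric drugs finds it named as allowed and has no prompt to look further.

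The first thing at stake is subject safety: avoidable exposure to a drug that the protocol elsewhere treats as high risk. The second is how the ECG data are read. Safety, including ECG parameters, is the primary endpoint (Section 9.7.1.1.1), and Section 9.7.1.8.5 counts subjects in QTcF outlier categories. A QTcF outlier, or a discontinuation under the QTcF stopping rules, could come from the co-medication and not from study drug. With about 15 subjects per arm (Section 9.7.2), one such subject is 1/15, or about 7% of an arm.

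**Working it through.** There is no planned figure to reproduce. The check is a drug-by-drug comparison of the listings, followed by the ECG and visit schedule.

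**1. Listing 1 against Listing 8.** Listing 1 names 30 drugs. Listing 8 names 17 under antipsychotics.

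| Drug | Listing 1 | Listing 8 |
|---|---|---|
| Chlorpromazine | prohibited | permitted |
| Haloperidol | prohibited | permitted |
| Mesoridazine | prohibited | permitted |
| Thioridazine | prohibited | permitted |

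The row "Thioridazine | Mellaril" appears in both. The other Listing 8 classes (antidepressants, mood stabilizers, benzodiazepines) share no drug with Listing 1. The overlap is therefore 4 of the 17 antipsychotics in Listing 8. Listing 1 prohibits 5 antipsychotics (these four and pimozide), so Listing 8 re-permits 4 of 5.

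**2. Can haloperidol's comment reconcile the two?** Its Listing 1 comment reads "When given intravenously or at higher than recommended doses, risk of sudden death, QT prolongation, and torsades increases". That describes when risk rises and does not confine the ban to those circumstances. Amiodarone's comment calls its torsades risk low, yet amiodarone is still prohibited, so comments do not narrow the prohibition. The other three drugs have no comment.

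**3. Listing 1 against Listing 7.** No drug named in Listing 7 is in Listing 1. Listing 7 does have two open entries: "Other opioids or opioid agonists which are used on PRN basis" and "Other benzodiazepines, tricyclic antidepressants, antipsychotics and other drugs which are used on PRN basis as sedatives". Neither carries a QT exception. Read literally, the first takes in methadone and levomethadyl, which Listing 1 classes as opiate agonists. The second takes in droperidol, which Listing 1 classes as a sedative. Because Listing 8 refers as-needed use to Listing 7, its open antipsychotic entry is also the route for as-needed use of the four drugs.

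**4. When would an ECG next be taken?** Scheduled on-treatment ECGs from Tables 7 and 14, in weeks since first dose of each phase:

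- Core Study: 2, 4, 8, 12, 26, 52, 78. The gaps are 2, 4, 4, 14, 26 and 26 weeks.
- OLE Phase: 0, 12, 26, 52, 78, 104. The gaps are 12, 14, 26, 26 and 26 weeks.

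The longest nominal gap is 26 weeks in both phases. Listing 8 asks for no ECG after a new start.

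**5. When would medications next be reviewed?** After Week 26, visits with concomitant-medication review are at Weeks 39, 52, 65 and 78 in the Core Study, and at Weeks 39, 52, 65, 78, 91 and 104 in the OLE Phase. That is every 13 weeks.

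**The case against.** The strongest reply is that the operative text already settles the matter. Section 9.4.7 bars the whole class of QT-prolonging drugs and allows new starts only if the drug is not otherwise prohibited. A subject already taking one of the four should fail exclusion 25 or 37. Exclusion 6 removes many subjects with psychiatric symptoms, and a QTc above 450 msec at Screening or Baseline excludes a subject in any case. During treatment, medications are reviewed at visits, unscheduled ECGs can be done, and Section 9.3.3 has QTcF stopping rules. On this view the error is an appendix slip that touches no endpoint definition, analysis or dose decision.

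Much of this stands, and it limits the risk. Continued use at entry is largely covered by the eligibility criteria. The 26-week ECG gap should not be read as 26 weeks of unnoticed exposure, because medication review should reveal a start within about 13 weeks. However, review helps only if the reviewer treats the drug as barred, and Listing 8 says that it is allowed. Entry checks cannot see a drug started later, and stopping rules act only when an ECG is taken. Appendix 2 invites a call to the medical monitor about drugs that are not listed, whereas these four are listed, as permitted.

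The Listing 7 point is weaker. A residual class does not naturally re-permit a drug barred by name, and nothing shows that methadone, levomethadyl or droperidol would be used as needed in this population. It is secondary, and the four-drug contradiction does not depend on it.

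**Conclusion.** The contradiction is real and Listing 8 is the side in error. Four drugs prohibited by name are permitted by name in the same appendix, with explicit allowance for new chronic use and no QT condition. Section 9.4.7 and the exclusion criteria show what was meant but do not remove the conflicting instruction.

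The practical exposure is mainly a new start during treatment, for up to 26 nominal weeks before the next scheduled ECG if begun just after Week 26 or a later one, and about 13 weeks before the next scheduled medication review. These intervals assume visits on their nominal dates and no unscheduled ECG. The protocol gives no rate of use of these drugs, so no expected number of affected subjects can be stated. The error should be fixed because the primary endpoint is safety, including ECG, and the correction is small.

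**What to change.** - Delete chlorpromazine, haloperidol, mesoridazine and thioridazine from Listing 8.
- At the head of the permitted listings, state that Listing 1 overrides Listings 7 and 8, including the open opioid, antipsychotic and sedative entries in Listing 7.
- Notify sites by memo.
- Query the recorded concomitant medications for the four drugs. Flag any exposed subject alongside the QTcF outlier tables, so that an outlier is not attributed to study drug without that information.

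The text change is four deleted rows and one sentence, plus a memo and one data query. Section 11.1 requires a written amendment or administrative change. If the correction is classed as affecting subject safety, it also needs regulatory submission and IRB approval, so it is best carried in the next amendment, with the site memo sent at once. The query uses data already collected.
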